8.1.3 Provider

Provider-level measures include mediators (OH knowledge and self-efficacy), a confounder (socio-demographic characteristics), and evaluation of implementation/fidelity (observation and audiotape of OH encounters) and adoption & maintenance (i.e. percentage of enrolled patients given a prescription and list of dentists).

- Providers' OH knowledge and self-efficacy to perform OH activities will be assessed through pre- and post-tests (Appendix E) administered before and after the didactic education session prior to WCV #1 (T_{-1}) and booster sessions before WCV #2 (T_2).
- Providers' socio-demographic characteristics (Appendix E) will be collected at the didactic training sessions prior to WCV#1 (T_{-1}).
- As an evaluation of the implementation/fidelity of the intervention, providers' oral health encounters will be observed or audiotaped by study staff and evaluated using the ParentProvider Communication Checklist (Appendix E), the same standardized skills checklist used during the skills training session (T_0 , T_3 , and T_6).
- Parent/caregivers will evaluate their provider's oral health communication and delivery of prescription and list of dentists on the A3: Parent exit questionnaire (Appendix E) completed at WCVs #1 - #3 (T_0 , T_3 , and T_6). This is also an evaluation of implementation/fidelity.
- Providers' EMR documentation of prescriptions and lists of dentists given will be audited throughout the main trial (T_0 , T_3 , and T_6), based on study arm. The percentage of enrolled caregivers who received the prescription and list of dentists will be calculated as an

evaluation of providers' adoption and maintenance of the provider-level intervention and recorded on the EMR Audit of Practice form (Appendix E).

- Providers will complete structured interviews with a trained moderator on implementation barriers/enablers to evaluate best strategies for dissemination of the oral health intervention. The interviews will be conducted at the pediatric practices at a time convenient for the provider and will contain interview questions to assess relative advantage of the OH intervention, compatibility of the OH intervention with the needs of the adopters, complexity of the OH intervention, trialability, and observability. Interviews will be conducted using zoom if in-person interviews are not possible due to the current COVID-19 outbreak.

8.1.4 Practice

Practice-level measures include mediators (organization readiness, organizational climate, and practice attitude) and evaluation of adoption and maintenance (percentage of enrolled patients with complete oral health documentation in EMR).

- Mediators of organization readiness and organization climate (Stamatakis et al., 2012) and practice attitudes toward adopting evidence-based interventions (EBI)(Aarons, 2004) will be assessed on the Practice Questionnaire (Appendix E) among leaders and providers from all 18 practices prior to enrollment of caregiver participants (T₋₁).
- Audits of providers' documentation of all 4 questions in EMR will be performed throughout the main trial (T₀, T₃, and T₆), based on study arm. The percentage of enrolled patients with complete documentation (i.e. all 4 questions) will be recorded on the EMR Audit of Practice form (Appendix E) and serve as an evaluation of the practice's adoption and maintenance of systematic documentation of OH in EMR for Arm A.

9 ASSESSMENT OF SAFETY

9.1 Specification of Safety Parameters

The principal investigator (PI) will report safety events for the study (unanticipated problems [UPs], adverse events [AEs], serious adverse events [SAEs]) to the Institutional Review Board (IRB) in accordance with the IRB's requirements as outlined below.

The PI will also report UPs involving risks to subjects to NIDCR. This will include UPs that meet the definition of a serious adverse event.

9.1.1 Unanticipated Problems

The Office for Human Research Protections (OHRP) considers unanticipated problems involving risks to subjects or others to include, in general, any incident, experience, or outcome that meets **all** of the following criteria:

- unexpected in terms of nature, severity, or frequency given (a) the research procedures that are described in the protocol-related documents, such as the IRB-approved research protocol and informed consent document; and (b) the characteristics of the subject population being studied;

- related or possibly related to participation in the research (“possibly related” means there is a reasonable possibility that the incident, experience, or outcome may have been caused by the procedures involved in the research); and
- suggests that the research places subjects or others at a greater risk of harm (including physical, psychological, economic, or social harm) than was previously known or recognized.

9.1.2 Adverse Events

OHRP defines an adverse event as any untoward or unfavorable medical occurrence in a human subject, including any abnormal sign (for example, abnormal physical exam or laboratory finding), symptom, or disease, temporally associated with the subject’s participation in the research, whether or not considered related to the subject’s participation in the research, (modified from the definition of adverse events in the 1996 International Conference on Harmonization E-6 Guidelines for Good Clinical Practice).

9.1.3 Serious Adverse Events

A serious adverse event (SAE) is one that meets one or more of the following criteria:

- Results in death
- Is life-threatening (places the subject at immediate risk of death from the event as it occurred)
- Results in inpatient hospitalization or prolongation of existing hospitalization
- Results in a persistent or significant disability or incapacity
- Results in a congenital anomaly or birth defect

An important medical event that may not result in death, be life threatening, or require hospitalization may be considered an SAE when, based upon appropriate medical judgment, the event may jeopardize the subject and may require medical or surgical intervention to prevent one of the outcomes listed in this definition.

9.2 Time Period and Frequency for Event Assessment and Follow-Up

Unanticipated problems, AE and SAEs will be recorded in the data collection system throughout the study. Events will be followed for outcome information until resolution or stabilization.

Given the nature of the interventions (EMR changes, education with skills training, and prescription + list of dentists) it is unlikely that intervention-related SAEs or AEs will occur. However, throughout the study, if a caregiver or provider reports an event to any study staff; it will be communicated to the PI immediately. The PI will record all reportable events occurring any time after informed consent is obtained until the last day of study participation.

9.3 Characteristics of an Adverse Event

9.3.1 Relationship to Study Intervention

To assess relationship of an event to study intervention, the following guidelines are used:

1. Related (Possible, Probable, Definite)
 - a. The event is known to occur with the study intervention.
 - b. There is a temporal relationship between the intervention and event onset.
 - c. The event abates when the intervention is discontinued.
 - d. The event reappears upon a re-challenge with the intervention.
2. Not Related (Unlikely, Not Related)
 - a. There is no temporal relationship between the intervention and event onset.
 - b. An alternate etiology has been established.

9.3.2 Expectedness of SAEs

Given the nature of the interventions (EMR changes, education with skills training, and prescription + list of dentists) it is unlikely that intervention-related SAEs or AEs will occur. The PI is initially responsible for determining SAE/AE expectedness, and NIDCR medical monitor/DSMB will then review and make their determination. An adverse event will be considered unexpected if the nature, severity, or frequency of the event is not consistent with the risk information previously described for the intervention.

9.3.3 Severity of Event

The following scale will be used to grade adverse events:

1. Mild: no intervention required; no impact on activities of daily living (ADL)
2. Moderate: minimal, local, or non-invasive intervention indicated; moderate impact on ADL
3. Severe: significant symptoms requiring invasive intervention; subject seeks medical attention, needs major assistance with ADL

9.4 Reporting Procedures

9.4.1 Unanticipated Problem Reporting to IRB and NIDCR

Incidents or events that meet the OHRP criteria for unanticipated problems require the creation and completion of an unanticipated problem report form. The following information will be included when reporting an adverse event, or any other incident, experience, or outcome as an unanticipated problem to the IRB:

- appropriate identifying information for the research protocol, such as the title, investigator's name, and the IRB project number;
- a detailed description of the adverse event, incident, experience, or outcome;
- an explanation of the basis for determining that the adverse event, incident, experience, or outcome represents an unanticipated problem;

- a description of any changes to the protocol or other corrective actions that have been taken or are proposed in response to the unanticipated problem.

To satisfy the requirement for prompt reporting, unanticipated problems will be reported using the following timeline:

- All unanticipated problems involving risks to subject or others must be reported to the UHCMC IRB within fourteen (14) calendar days of discovery of the problem or event. The only exception to the above timeframe is for the reporting of deaths. All internal, unexpected, study-related deaths must be reported to the IRB within seven calendar days of their discovery. Reporting to NIDCR and the CC must also occur within 7 calendar days if death or a life-threatening event occurs or within 14 calendar days for all other SAEs.

The following are examples of unanticipated problems that need to be reported by the PI to the UHCMC IRB as soon as possible, but in all cases within 14 calendar days:

- Adverse events, which in the opinion of the PI, are **both** unexpected and related or possibly related.
 - An adverse event is “unexpected” when its specificity and severity are not accurately reflected in the IRB approved informed consent document.
 - An adverse event is “related to the research procedures” if in the opinion of the PI, it was more likely than not to be caused by the research procedures, or if it more likely than not that the event affects the rights and welfare of current participants.
 - All fatal events determined to be not study-related and expected should be kept in the PI’s file and do not need to be reported to the IRB.
 - All fatal events determined to be not study-related and unexpected must be reported to the IRB at the next continuing review or study closure, whichever is first.
- Information that indicates a change to the risks or potential benefits of the research.
- A breach of confidentiality including inappropriate disclosure, lost or stolen confidential information.
- Changes to the protocol taken without prior IRB review to eliminate apparent immediate hazard to a research participant.
- Incarceration of a participant in a protocol not approved to enroll prisoners.
- Event that requires prompt reporting to the sponsor such as disqualification or suspension of investigator.
- Complaint of a participant when the complaint indicates unexpected risks or the complaint cannot be resolved by the research team.

Protocol deviation (including accidental or intentional protocol deviation) that caused harm to participants or others or indicates participants or others are at increased risk of harm. All UPs should be reported to appropriate institutional officials (as required by an institution’s written reporting procedures), the supporting agency head (or designee), and OHRP within one month of the IRB’s receipt of the report of the problem from the PI.

All UPs will be reported to NIDCR’s centralized reporting system via Rho Product Safety, and to the CC:

- Product Safety Fax Line (US): [name]

- Product Safety Fax Line (International): [contact]
- Product Safety Email: [contact]
- CC Safety Email: [contact]
- CC Safety Fax Line: [name]

General questions about UP reporting can be directed to the Rho Product Safety Help Line (available 8:00AM – 5:00PM Eastern Time):

- US: [name]
- International: [contact]

9.4.2 Serious Adverse Event Reporting to NIDCR

Any AE meeting the specified Serious Adverse Event criteria will be submitted on an SAE form to NIDCR's centralized safety system via Rho Product Safety. This report may be sent by fax or email. Once submitted, Rho Product Safety will send a confirmation email to the investigator within 1 business day. The investigator should contact Rho Product Safety if this confirmation is not received. This process applies to both initial and follow-up SAE reports.

SAE Reporting Contact Information:

- Product Safety Fax Line (US): [name]
- Product Safety Fax Line (International): [contact]
- Product Safety Email: [contact]

General questions about SAE reporting can be directed to the Rho Product Safety Help Line (available 8:00AM – 5:00PM Eastern Time):

- US: [name]
- International: [contact]

The study clinician will complete a Serious Adverse Event Form and submit via fax or email within the following timelines:

- All study-related deaths and immediately life-threatening events, , will be recorded on the Serious Adverse Event Form and submitted to Product Safety within 7 calendar days of site awareness.
- Study-related serious adverse events other than death and immediately life-threatening events, will be reported by fax within 14 calendar days of site awareness.

All SAEs will be followed until resolution or stabilization.

10 STUDY OVERSIGHT

In addition to the PI's responsibility for oversight, study oversight will be under the direction of a Data and Safety Monitoring Board (DSMB) composed of members with appropriate clinical, statistical, scientific, and ethical expertise. The NIDCR will appoint the Board. The DSMB will

meet at least annually to assess safety and effectiveness data, study progress, and data integrity for the study. If concerns arise, more frequent meetings may be held. The DSMB will operate under the rules of an NIDCR-approved charter that will be approved at the organizational meeting of the DSMB. The DSMB will provide recommendations to the NIDCR.

11 CLINICAL SITE MONITORING

Clinical site monitoring is conducted to ensure that the rights of human subjects are protected, that the study is implemented in accordance with the protocol and/or other operating procedures, and that the quality and integrity of study data and data collection methods are maintained. Monitoring for this study will be performed by NIDCR's Clinical Research Operations and Management Support (CROMS) contractor. The monitor will evaluate study processes and documentation based on NIDCR standards and the International Conference on Harmonisation (ICH), E6: Good Clinical Practice guidelines (GCP).

Details of clinical site monitoring will be documented in a Clinical Monitoring Plan (CMP) developed by the CROMS contractor, in collaboration with the NIDCR Office of Clinical Trials and Operations Management (OCTOM) and the NIDCR Program Official. The CMP will specify the frequency of monitoring, monitoring procedures, the level of clinical site monitoring activities (e.g., the percentage of subject data to be reviewed), and the distribution of monitoring reports. Some monitoring activities may be performed remotely, while others will take place at the study site(s). Staff from the CROMS contractor will conduct monitoring activities and provide reports of the findings and associated action items in accordance with the details described in the CMP. Documentation of monitoring activities and findings will be provided to the site study team, the study PIs, OCTOM, and the NIDCR. The NIDCR reserves the right to conduct independent audits as necessary.

12 STATISTICAL CONSIDERATIONS

12.1 Study Hypotheses

We hypothesize that providers with improved knowledge regarding the chronicity of caries and appropriate skills training (through bundled provider- and practice-level interventions) will deliver consistent reinforcing oral health facts to parents (at annual WCVs) that will result in increased dental utilization for their child compared to those providers delivering usual care based on AAP education.

12.2 Sample Size Considerations

The study design will involve a cluster randomization to two arms:

1. Bundled (Practice + provider) interventions, 2. Enhanced usual care. The assumed response rates (proportion of children who have dental attendance) are Arm A: 0.46 (The dental utilization reported among Medicaid-enrolled children by Vujicic and Nasseh, 2015 was 48%, but we used 46% to be conservative), Arm B: 0.30 (based on pilot study where 30% of parent reported routine dental visit for child in the past year).

Eighteen practices (comprising the clusters) will be included in the study. Practices will be randomized to one of the two arms using a restricted randomization scheme with the constraint that 9 practices will be assigned to each arm. This approach will involve the computation of a balance score (for each candidate randomization) based on marginal differences in three key practice-level variables: % Medicaid-enrolled patients [20% to 40% and >40%], ratio of patients to providers, county [Cuyahoga vs. other]. We use the first generated (constrained) randomization that provides good balance according to a pre-selected balance criterion; it may be reasonable to require perfect marginal balance, if (as we expect) there are a reasonably large number of randomizations that yield this.

The primary objective is to compare dental care attendance between the two arms. For simplicity in the power calculation we consider the binary outcome of any dental attendance in the two year period of follow-up. Dental attendance will be based on a single summary score (number of years - out of two - in which the child visits the dentist at least once a year). We thus suppose the use of a two-sided 0.05 alpha level z test (with pooled variance) for a difference in proportions. We assume, as a rough approximation, that the study will recruit an equal number of patients in each practice. Making conservative allowances for an intra-cluster (within-practice) correlation (ICC: in the binary dental attendance outcome) of 0.04 and a 25% drop-out rate, a sample size of 512 participants per arm (total n= 1024) will provide an estimated 80% power to detect the above difference in proportions. Alternatively, this sample size (actually 438 per group) will provide 90% power to detect this same effect size if the ICC is only 0.02. If the intervention effect is only 0.12 (0.42 versus 0.30), a sample size of 457 per group (914 total) will still provide 80% power with a dropout rate of 25% if the ICC is only 0.01. For the purposes of this study, a sample size of 512/arm (n=1024) will be recruited.

For sample size estimates, an important secondary outcome will be incidence of new decayed or filled teeth (dft). Mean dft is hypothesized to decrease for Arm A relative to Arm B. Our

previous data (Lee et al. 2015) among 5 to 7 year old low-income children suggests a mean dft for usual care of 4.5 (standard deviation = 7) which we assume to be a reasonable value for the enhanced usual care arm in the present study. We assume the same standard deviation for the new intervention group, assuming normally distributed responses for the power calculation. In fact, as dft is a count (possibly following a distribution such as Poisson or negative binomial) it is likely that the standard deviation will decrease with the mean, making our approach conservative (McCullagh and Nelder 1989).

We suppose the use of a two-sided 0.05 alpha level t test, to test for a difference in mean dft between the two groups. As done for the primary outcome, we assume an equal number of patients in each practice and allow for 25% dropout. For dft, a robust clinical outcome, we use a smaller ICC of 0.02. Then for the planned recruitment sample of 512 per arm, we will have 74% power to detect a 40% decrease in the mean dft (i.e., a mean dft of 2.7 in the Bundled intervention arm). If the ICC is only 0.1, this power will increase to 84%.

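### The dft power statement pairs 84% power with an ICC of 0.1; by the plan's own assumptions 0.1 gives about 34%, and 84% fits 0.01, so the ICC is probably a misprint.

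*Combined protocol and SAP*

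**What the plan says.** The power calculation for dft is at the end of section 12.2 (Sample Size Considerations) of the combined protocol and SAP, where dft is presented as an important secondary outcome. The test is stated as follows: "We suppose the use of a two-sided 0.05 alpha level t test, to test for a difference in mean dft between the two groups". The control mean is 4.5 and the SD is 7, with the same SD taken for the intervention arm. The target is a 40% reduction, to a mean of 2.7. Practices are assumed to be of equal size and dropout is 25%, as for the primary outcome.

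For clustering, the plan says "we use a smaller ICC of 0.02", and at 512 recruited per arm "we will have 74% power to detect a 40% decrease in the mean dft". The next sentence gives the alternative scenario: "If the ICC is only 0.1, this power will increase to 84" percent.

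Earlier in the same section, two alternatives for the primary outcome are worded in a similar way. One "will provide 90% power to detect this same effect size if the ICC is only 0.02"; the other "will still provide 80% power with a dropout rate of 25% if the ICC is only 0.01". Both use an ICC below the primary-outcome base value of 0.04.

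**The concern.** An ICC of 0.1 is five times the dft base value of 0.02. With the number of practices, children per practice, effect and SD held fixed, raising the ICC inflates the variance and reduces power. The sentence claims the opposite, and its wording (a low ICC, a gain in power) only makes sense for a value below 0.02. Either the ICC or the power is wrong.

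Taken at face value, the sentence tells a reader that dft power survives strong clustering and even improves under it. It follows a base-case power that is already below 80%, so it is the line a reader would look to for reassurance about this outcome. It could also be carried into a later trial's planning as it stands.

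**Working it through.** **Inputs, all from section 12.2**

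- Difference in means: 4.5 − 2.7 = 1.8; common SD 7; two-sided alpha 0.05, t test.
- Recruited 512 per arm; 25% dropout leaves 0.75 × 512 = 384 analysed per arm.
- 9 practices per arm, equal sizes: m = 384/9 = 42.67 children per practice.

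**Method**

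The section prints no formula, so this is a reconstruction using the standard one: design effect DE = 1 + (m − 1) × ICC; effective n per arm = 384/DE; SE of the difference = 7 × √(2/effective n); power from the noncentral t with noncentrality 1.8/SE and 2 × (effective n) − 2 degrees of freedom.

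**Step 1: does the method reproduce the plan's other figures?**

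Primary outcome, pooled-variance z test for two proportions, 25% dropout, 9 practices per arm:

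| Comparison | Recruited per arm | ICC | m | DE | Effective n per arm | Power | Plan |
|---|---|---|---|---|---|---|---|
| 0.46 vs 0.30 | 512 | 0.04 | 42.67 | 2.667 | 144.0 | 80.2% | 80% |
| 0.46 vs 0.30 | 438 | 0.02 | 36.50 | 1.710 | 192.1 | 90.1% | 90% |
| 0.42 vs 0.30 | 457 | 0.01 | 38.08 | 1.371 | 250.0 | 80.0% | 80% |

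All three agree.

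**Step 2: dft at the base ICC and at the two candidate values**

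| ICC | DE | Effective n per arm | SE | 1.8/SE | Power | Plan |
|---|---|---|---|---|---|---|
| 0.02 | 1 + 41.67 × 0.02 = 1.833 | 209.5 | 0.684 | 2.63 | 74.7% | 74% |
| 0.01 | 1 + 41.67 × 0.01 = 1.417 | 271.1 | 0.601 | 2.99 | 84.8% | not printed |
| 0.1 | 1 + 41.67 × 0.1 = 5.167 | 74.3 | 1.148 | 1.57 | 34.4% | 84% |

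The base case reproduces to within a point. The disputed figure misses by about 50 points at the printed ICC and by less than one point at 0.01. Solving for a power of exactly 84% gives an ICC of 0.0108.

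If each practice is cut to 42 whole children (378 per arm), power is 74.4% at ICC 0.02 and 84.4% at 0.01. Ordinary rounding then gives the plan's 74% and 84%.

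**Step 3: can another convention rescue 84% at ICC 0.1?**

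- Cluster size taken before dropout (56.89): 28%.
- No dropout: 36%.
- Dropout applied as 512/1.25: 35%.
- One-sided test: 47%.
- 16 cluster-level degrees of freedom: 31%, or 26% with the pre-dropout cluster size.

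None comes near 84%. There is also a ceiling: as children per practice grow without limit, effective n per arm tends to 9/0.1 = 90, where power is about 40%. With 9 practices per arm and an ICC of 0.1, no amount of enrolment reaches 84%.

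**The case against.** The strongest reply is that this is a dropped zero and nothing more. The design value for dft is ICC 0.02 with 74% power, which reproduces. The sample size is set by the primary outcome at ICC 0.04. Nothing in section 12.4 uses the 0.1 or the 84%. A statistically trained reader would see from the wording that a value below 0.02 was meant, so few would be misled, and the 34% describes a scenario nobody planned. The design-effect formula and degrees of freedom are also inferred, and because the text was extracted from a PDF, a digit lost in extraction cannot be wholly excluded.

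Most of this is fair on scale. No design or analysis decision turns on the sentence, and 34% matters only if 0.1 was really intended. It does not remove the error: the pairing is wrong as written, and nothing else in the documents corrects it. The inferred method matches four other printed figures, and the direction of the error needs no formula. Loss in extraction is possible but unsupported: the sentence is otherwise intact, and 0.01 came through correctly earlier in the same section. Not every reader of a power statement for a named outcome will make the mental correction.

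**Conclusion.** The concern holds. An ICC of 0.1 with 84% power is impossible under the section's stated assumptions: 0.1 gives about 34%, and 84% corresponds to an ICC of about 0.01. That 0.01 was intended is an inference, but a strong one, resting on the sentence's own wording, the numerical match, and the use of 0.01 for the primary outcome. On that reading the 84% stands and only the ICC is wrong.

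The figures assume equal practice sizes, 384 analysed per arm, SD 7 in both arms and the standard design effect. The practical reach is small: one sensitivity statement for a secondary outcome, with no effect on the 1024 total, the primary-outcome power or any planned analysis.

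**What to change.** Ask the study statistician to confirm the intended ICC against the original calculation. If it was 0.01, replace 0.1 with 0.01 in section 12.2 and leave 84% as it is. If 0.1 was meant, give the power as about 34% and remove the words that present it as a low ICC and a gain in power. Stating the design-effect formula and the analysed number per practice alongside would let a reader check the result. This is a one-line correction with no operational cost and no change to sample size.
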